	
mm and angulation among others⁸. From a recent Consensus Conference, the influence of each characteristic on early or late EVAR failure is not clear, but hostile neck morphology is generally associated with higher rates of aneurysm-related adverse events and mortality⁹. A recent independent Expert Panel, applying the Delphi methodology Indeed, agreed to define 10 mm as the threshold value below which standard EVAR should not be considered feasible⁹. Moreover, the same experts agreed on the fact that an angulation above 60° is considered a hostile criterion for EVAR procedure. Finally should be considered that some “hostility” factors can be present at the same time and creating the ideal condition for EVAR failure⁹. The issue linked to the anatomical not feasibility of standard EVAR in patients not eligible for OR can be solved with custom made devices (CMD), but they were limited by high production costs and long time for creations (10-12 weeks)¹⁰. Nowadays no one off-the-shelf device aimed to overcome neck hostility in AAA is available on the market.
 
The present study aims at evaluating the anatomical applicability of an off-the-shelf scalloped stent-graft (Treovance, Terumo Aortic) to treat infrarenal AAA with a short and/or angulated neck.

Schedule	
Step 1: Ex-Vivo phase
 
 - Step 1.0: Protocol proposal and CE approval - Step 1.1: CTA measurement - Step 1.2: CTA data analysis - Step 1.3: Models fitness evaluation

	
 - Step 1.4: Preliminary publication and endograft production
STUDY DESIGN	Step 1-Single center retrospective observational study on the anatomical applicability in the coordinator center of an off-the-shelf scalloped device to treat infrarenal AAA with short and/or angulated neck.

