EX VIVO AND IN VIVO TREATMENT	
Step 1: All patients affected by AAAs and electively treated with EVAR or OR in the Vascular Surgery Unit of Modena e Reggio Emilia from 2010 to 2020 were considered eligible for the ex-vivo feasibility study. Preoperative contrast-enhanced computed tomography scans (CTAs) were independently reviewed by 2 vascular surgeons (investigators) experienced in the planning of aortic procedures using a dedicated workstation with dedicated vascular software (EndoSize, Thereva). Multiplanar and curved reconstructions of each CTA were used to assess the required measurements. In addition to standard measurement taken to plan an EVAR procedure the center-lumen-line distance from the inferior margin of the upper renal artery to the inferior margin of the lower renal artery was taken in order to estimate the gain of neck length permitted with the scallop. An inter-examiner or intra-examiner error of 5% was accepted. In case of a variation >5%, a third investigator of the study would independently reanalyze the CTA. To study the suitability of the device, 2 different endograft models were constructed and fitted in the CTA-based

	measurements made as described to evaluate the anatomical feasibility of these models.
INCLUSION CRITERIA	
Step 1:
 
 - Patients Electively treated with EVAR or AAA at the coordinator center - Age >18 -Both sex -Preoperative 2.5mm CTA available -Written informed consent.
SAMPLE SIZE	Step 1: No statistical analysis of the sample size was carried out. Considering the number of AAA treated in the coordinator center each year and analyzing a time interval of 10 years a sample size of 1000 CTA was estimated. This number should be sufficient to carry out the anatomical feasibility analysis.
OUTCOMES/ENDPOINTS	
Step 1
 
Outcome: Anatomical feasibility evaluation

STATISTICAL ANALYSIS	To study the suitability, 2 different endograft designs were constructed. The preoperative measurements were made according to a previously described methodology. The models were matched with each preoperative CTA measure in order to evaluate if they fit or not in the index patients. Continuous variables are expressed as mean, and standard deviation and

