	
differences were tested with the two-sided t-test or the Mann-Whitney U-test, if appropriate. Categorical variables are expressed as counts and percentages and the chi-square test or Fisher's exact test was used for analysis. All data were entered into the logistic regression model if they had a univariable P-value of <0.05. Data resulted significant in this model were put in a multivariate one. In the multivariable analyses, clinical factors or potential confounding variables were expressed as odds ratio with 95% confidence interval (CI). The goodness of fit of the logistic regression models has been assessed calculating the C-statistic.. The analysis was carried out using STATA 14.

REFERENCES	

- | | |
|--|---|

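### The C-statistic, the only goodness-of-fit check named for the logistic models, measures discrimination and cannot show that they fit (minor; secondary regression only)

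*Combined protocol and SAP*

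**What the plan says.** All references are to the combined protocol and SAP.

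- **Model assessment (STATISTICAL ANALYSIS).** One sentence covers it: "The goodness of fit of the logistic regression models has been assessed calculating the C-statistic". No section names a calibration measure, a residual check, a linearity check or internal validation.
- **How the models are built (same section).** "All data were entered into the logistic regression model if they had a univariable P-value of <0.05". Then: "Data resulted significant in this model were put in a multivariate one". Results are reported as odds ratios with 95% CIs.
- **How suitability is decided (same section).** "The models were matched with each preoperative CTA measure in order to evaluate if they fit or not in the index patients". This is a direct comparison of two graft designs with each patient's measurements; no regression is involved.
- **Continuous measurements.** EX VIVO AND IN VIVO TREATMENT adds a distance between the renal arteries, taken "in order to estimate the gain of neck length permitted with the scallop".
- **Cut-offs mentioned.** RATIONAL reports that an expert panel "agreed to define 10 mm as the threshold value below which standard EVAR should not be considered" feasible, and that "an angulation above 60° is considered a hostile criterion for EVAR procedure". It adds that such "factors can be present at the same time".

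The plan does not state the dependent variable of the logistic models, the candidate factors, whether measurements enter as linear terms, categories or transformations, or any cut-off for the scalloped designs.

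**The concern.** Goodness of fit asks whether predicted risks agree with observed risks across the range of the predictors, and whether the assumed shape of each effect is right. The C-statistic asks something else: how often a patient with the outcome is ranked above one without it. A high C can therefore be reported as good fit when the shape of an effect is wrong.

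This is plausible here. Suitability is decided by matching a device to measurements, and such matching tends to work through cut-offs. If neck length or angulation were then entered as a straight line, the model would replace a jump by a slope. At stake is the meaning of a reported odds ratio: a constant multiplier per mm would be published for an effect that may sit almost wholly at one value, and the C-statistic would give no warning.

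**Working it through.** **The plan's own figure.** The only number is the 1000 CTA in SAMPLE SIZE. It cannot be reproduced, since no annual volume is given; 1000 over 10 years implies 1000/10 = 100 a year. It is used below only as n.

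**Step 1: what C responds to.** With n1 patients with the outcome, n0 without, and R1 the sum of the ranks of the predictions in the first group,

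C = [R1 − n1(n1+1)/2] / (n1 × n0).

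Only ranks appear, so any strictly increasing change to the predictions leaves C exactly as it was. This needs no assumption. In one simulated data set of 1000, replacing the correct linear predictor lp by 3 × lp + 1.5 gave:

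| | Correct risks | Distorted risks |
|---|---|---|
| C | 0.773 | 0.773 |
| Mean predicted (observed 0.426) | 0.410 | 0.513 |
| Hosmer-Lemeshow chi-square | 7.6 (P=0.47) | 1580 (P<0.001) |

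**Step 2: one measurement entered as a straight line.** Assumed inputs: neck length gamma with shape 4 and scale 5 (mean 4 × 5 = 20 mm, SD √4 × 5 = 10 mm). Two truths are compared, each fitted with logit(p) = a + b × length:

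- Linear: logit(p) = 0.1395 × (length − 20), so the odds ratio per mm is exp(0.1395) = 1.15.
- Step: p = 0.10 below 10 mm and 0.90 from 10 mm.

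| | Linear truth | Step truth |
|---|---|---|
| C of the fitted line | 0.79 | 0.79 |
| Fitted odds ratio per mm | 1.15 | 1.15 |
| Predicted / observed, 7-10 mm (about 9% of patients) | 0.17 / 0.17 | 0.54 / 0.10 |
| Linearity test rejects | about 5% of runs | 100% of runs |

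In the step case the true odds ratio across 10 mm is (0.90/0.10)/(0.10/0.90) = 81, and for any 1 mm difference on one side of it the odds ratio is 1. The reported 1.15 per mm describes neither, and C does not reveal this.

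**Step 3: range over other assumptions.**

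- Weaker step, 0.30/0.70 at 10 mm: C 0.61; 0.55 predicted against 0.30 observed at 7-10 mm.
- Step 0.10/0.90 at 7 or 15 mm: C 0.67 or 0.89; in the 3 mm below the cut-off, 0.73 or 0.39 predicted against about 0.10 (4.5% or 13.2% of patients).
- Two independent predictors with steps at 10 mm and 60°, log odds ratio 1.7 each: C 0.68; 0.65 predicted against 0.43 at 7-10 mm. A truly linear two-predictor model with the same C of 0.68 gives 0.37 against 0.37.
- If the outcome is device fit (length plus scallop gain at least 10 or 15 mm, angle up to 60°, 5% of results flipped): C 0.88 or 0.86; about 0.65 or 0.45 predicted against 0.05 in the 3 mm below the cut-off (about 3.4% or 8.7% of patients). Without the flip, C is 0.95 or 0.91.

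**Step 4: does the remedy detect the problem?** A four-knot spline test rejected linearity in 97-100% of single-predictor 0.10/0.90 runs and 93-100% of two-predictor runs, against 3-9% when the line was right. A ten-group calibration test found the single-predictor misfit at 10 mm in 100% of runs, but the two-predictor misfit (independent, log odds ratio 1 to 2) in only 23-37%. The linearity check is therefore the main one.

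**The case against.** The strongest objection is that the plan reports odds ratios, not predicted risks, and that nothing is decided from the model. Suitability is settled by direct matching, so an error near a cut-off in the regression cannot misclassify anyone. The second half stands and limits the point. The first half does not remove it: in step 2 the odds ratio itself is 1.15 per mm under both truths and misdescribes one of them.

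Second, the form of entry is not stated. This also stands. The linearity concern applies only to measurements entered as linear terms; if they enter as categories at the true cut-off, the illustration falls away. C would still not be a measure of fit.

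Third, apart from n=1000 every input is assumed, and the large gaps sit in narrow bands, about 3-9% of patients in the 10 mm examples. That is fair. The ranges show how much the gap varies; step 1 needs none of these inputs.

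A reader might go further in several ways that the documents do not support:

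- *That the feasibility result is unreliable.* It is a count of fits and does not pass through the regression.
- *That 10 mm and 60° are the cut-offs of the scalloped designs.* RATIONAL gives them for EVAR, the 10 mm specifically for standard EVAR. They are examples here.
- *That C can never expose misfit.* With several predictors, comparing C between model forms can: 0.68 for lines against 0.72 for steps in the two-predictor case. The plan makes no such comparison.
- *That the P<0.05 screening undermines the analysis.* It is a separate, smaller matter. With independent candidates, a true odds ratio of 1.5 is reported as 1.50-1.53. With three strong factors and a 30% outcome share, C is too high by 0.006-0.014. It is larger only in less favourable settings, up to 0.034-0.074 with 20 candidates and one weak factor.

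**Conclusion.** Wrong as written, minor. The named method cannot do what the sentence says, and nothing else in the plan does it. That conclusion rests on the definition of the C-statistic and is firm.

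The size is illustrative. It depends on an assumed distribution of neck length, an assumed step and linear entry, none of which the documents give. Under those assumptions, C 0.79 with an odds ratio of 1.15 per mm is compatible both with a model that fits and with one that predicts 0.54 where 0.10 is observed. The consequence is confined to the interpretation of the secondary regression. If the dependent variable is device fit, it is derived from the same measurements that predict it, so C may approach 1 and separation may occur by construction. That is a further reason to define it before interpreting C.

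**What to change.** In STATISTICAL ANALYSIS:

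1. Report the C-statistic as discrimination, not as goodness of fit.
2. State the dependent variable of the logistic models and how each CTA measurement enters them (linear, categories with stated limits, or transformed).
3. For each measurement entered as a linear term, test and plot linearity in the logit, for example with restricted cubic splines, and change the form if it fails.
4. Add a smoothed calibration plot.
5. As a minor addition, if P<0.05 selection is kept, also report a C corrected for optimism by a bootstrap that repeats the selection steps.

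**Cost.** A revised paragraph and a few lines of code; no new data. Confidence intervals may widen and the reported C may fall slightly. The remedy is partial: at a sharp step, a five-knot spline lowers the prediction at 7-10 mm from 0.54 to 0.30 against 0.10 observed. The spline test also has little power when few patients lie below the cut-off (34% for a 0.30/0.70 step at 5 mm).

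### The C-statistic is an apparent value, taken in the data that chose and fitted the predictors with no internal validation, so it is biased upward by an amount the plan does not fix (minor, cheap to correct)

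*Combined protocol and SAP*

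**What the plan says.** The Statistical Analysis section describes selection in two steps. In the first, "All data were entered into the logistic regression model if they had a univariable P-value of <0.05". In the second, "Data resulted significant in this model were put in a multivariate one". Results are given as odds ratios with 95% confidence intervals. The only model-performance figure is the C-statistic: "The goodness of fit of the logistic regression models has been assessed calculating the C-statistic".

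The Study Design section describes Step 1 as a "Single center retrospective observational study on the anatomical applicability in the coordinator center", and no other data set is named. Under Sample Size, "a sample size of 1000 CTA was estimated" from centre volume over ten years, and "No statistical analysis of the sample size was carried out".

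The plan does not give the dependent variable of the regression, the number of candidate predictors, the expected event share or the significance level of the second step. It mentions no internal or external validation and no correction for optimism.

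**The concern.** A model selected and fitted in one data set separates outcomes better in that data set than in new patients, because the selection and the coefficients have partly followed its chance features. A C-statistic computed there inherits the excess. That the plan computes it on the same patients is an inference, but with a single cohort named it is the only reading the text supports.

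This is separate from the label. The C-statistic measures discrimination, not goodness of fit, but renaming it would leave the number just as biased.

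At stake is the one performance figure the plan will report. It could be read as how well the selected factors would work elsewhere, and it would be too favourable for that use.

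**Working it through.** **The plan's own figure.** The only number stated is 1000 scans over ten years, which implies 1000/10 = 100 a year. No yearly volume, effect size or precision target is given, so it cannot be reproduced by formula. No C-statistic or event count is stated.

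**Inputs from the documents.** N = 1000 (Sample Size); two-sided univariable tests, a screen at P<0.05 and a second selection by significance (Statistical Analysis).

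**Inputs assumed.** 10 to 30 independent normal candidates; 0, 3 or 5 true predictors; event share 5% to 50%; 0.05 for the second step.

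**Method.** For each simulated data set: t-test screen, logistic fit on the survivors, keep terms with Wald P<0.05, refit. Optimism = mean of (C in the same data − C in a large sample of new patients).

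**Simulation A** (400 data sets per setting, 20,000 new patients, N = 1000, 30% events):

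| True predictors | Apparent C | C in new patients | Optimism, 15 candidates | Optimism, 30 candidates |
|---|---|---|---|---|
| 3 weak, OR 1.22 per SD | 0.60–0.61 | 0.58 | 0.026 | 0.031 |
| 5 moderate, OR 1.35 per SD | 0.68 | 0.66–0.67 | 0.013 | 0.026 |

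**Simulation B** (150 data sets per setting, 40,000 new patients, N = 1000; Monte Carlo error about 0.001 to 0.003; data sets with no surviving predictor left out). Cells are optimism by event share:

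| Candidates; true predictors (log-odds per SD) | C in new patients | 5% | 10% | 20% | 30% | 50% |
|---|---|---|---|---|---|---|
| 10; 3 (0.4) | 0.65–0.68 | 0.0364 | 0.0160 | 0.0061 | 0.0019 | 0.0021 |
| 20; 3 (0.4) | 0.65–0.68 | 0.0526 | 0.0233 | 0.0131 | 0.0138 | 0.0058 |
| 30; 3 (0.4) | 0.64–0.68 | 0.0723 | 0.0409 | 0.0169 | 0.0182 | 0.0076 |
| 20; 5 (0.3) | 0.62–0.67 | 0.0749 | 0.0345 | 0.0170 | 0.0175 | 0.0099 |
| 20; 3 (0.8) | 0.80–0.81 | 0.0184 | 0.0134 | 0.0075 | 0.0056 | 0.0013 |
| 20; 3 (1.5) | 0.90–0.93 | 0.0073 | 0.0074 | 0.0014 | 0.0033 | 0.0017 |
| 20; none | 0.50 | 0.1109 | 0.0900 | 0.0640 | 0.0535 | 0.0515 |

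The two simulations agree where they meet. Log-odds 0.3 is OR exp(0.3) = 1.35. With five such predictors and 30% events, B gives 0.0175 at 20 candidates, between A's 0.013 (15) and 0.026 (30).

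**Fewer usable scans.** With some true signal, B gives 0.001 to 0.137 at N = 500 and 0.006 to 0.204 at N = 250, across all event shares.

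**No true predictors.** The chance that at least one of 30 independent null candidates passes the screen is 1 − 0.95^30 = 0.785. This matches the 78% of data sets in A that still produced a model, with mean apparent C 0.56 against a true 0.50.

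**Does the second round add to the bias?** With 30 candidates, weak signal and 200 data sets per setting, optimism at N = 1000 was 0.078 with all candidates kept, 0.034 after one round and 0.032 after two. At N = 400 it was 0.151, 0.080 and 0.076. The second round raised it in none of 16 settings.

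**How well does the correction work?** Bootstrap with selection repeated (100 data sets, 60 resamples each, 30 candidates, N = 1000):

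| Signal | Apparent | True | Corrected | Error before | Error after |
|---|---|---|---|---|---|
| Weak | 0.605 | 0.575 | 0.561 | +0.030 | −0.014 |
| Moderate | 0.684 | 0.665 | 0.655 | +0.019 | −0.010 |

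**The case against.** **Little rests on this number.** The stated outcome is anatomical feasibility. The regression is secondary, is reported as odds ratios, and has no stated prediction aim, score or decision threshold. This stands, and it is why the point is minor.

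**The signal may be strong.** The graft models are matched to the scan measurements "in order to evaluate if they fit or not in the index patients". If that result is the dependent variable and the same measurements are candidates, C could be high and the optimism small: 0.001 to 0.007 in Simulation B at a true C of 0.90 to 0.93. The plan leaves this open. On that reading circularity or separation would be the larger problem, but it would not make an uncorrected C sound.

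**The simulated rule may not be the plan's rule.** The text can also be read as univariable logistic models followed by one multivariable model. The exact figures would then change; the upward direction would not.

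**The correction is imperfect.** In the check above about half the error remained, with the opposite sign (0.014/0.030 and 0.010/0.019). This also stands, and it is the reason to show both values.

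A reader might infer three stronger claims that the documents do not support:

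- *That the bias has a known range reaching about 0.07.* At N = 1000 with some true signal, values near that level arose only with few events (5%) and weak predictors. They also arise if the analysis set is cut to 0.40 × 1000 = 400, using the background figure for patients unsuitable for EVAR. That figure does not define the analysis set: patients treated electively by either EVAR or open repair are eligible, and the models are matched to every scan.
- *That two rounds of P-value selection make the bias worse than one.* The comparison above shows otherwise. Selection adds optimism relative to a small prespecified model, not relative to fitting every candidate.
- *That the feasibility result is affected.* It does not depend on the C-statistic.

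**Conclusion.** The point holds as a minor one. The planned C-statistic is an apparent value. It was biased upward in every setting of Simulations A and B, and the plan has no step to estimate or remove the excess, which comes from selecting and fitting in the same data.

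The size cannot be fixed from the documents. At 1000 scans, with 30% events and 15 to 30 candidates, it is about 0.01 to 0.03 for weak or moderate predictors (C in new patients roughly 0.58 to 0.68). With only 10 candidates, or about half the patients having the event, it can be under 0.01 even there. With strong predictors it is under 0.01. It reaches 0.036 to 0.075 with 5% events and weaker predictors (C about 0.62 to 0.65), and 0.05 to 0.11 with no true predictors. It tends to grow if fewer scans are usable.

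All of these figures rest on independent normal candidates and a 0.05 threshold at the second step, neither of which the plan states.

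**What to change.** Add to the Statistical Analysis section: the C-statistic is corrected for optimism by bootstrap, with at least 500 resamples of patients; the univariable screen, the second selection and the final fit are all repeated in each resample.

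C_corrected = C_apparent − mean over resamples of (C of the resample's model in the resample − C of that model in the original data)

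A resample in which nothing is selected counts as 0.50 in both terms. Report the apparent and corrected values side by side, and describe both as discrimination rather than goodness of fit.

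For the procedure to be repeatable, the plan must also name the dependent variable, the candidate list and the threshold of the second step.

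**Cost.** A few lines of Stata and a short addition to the plan; no new data or staff. The reported C becomes slightly lower, and at N = 1000 the correction may overshoot by about 0.01. It does nothing for odds ratios distorted by selection, which are a separate matter. If the optimism proves negligible, the study will have shown so from its own data.
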